3.1 Analysis Software

All analyzes will be carried out on the Statistical Analysis System (SAS[®]) Analytics Pro, version 9.4 including statistical procedures in the SAS/STAT[®] version 14.1 module [9].

3.2 Descriptive Statistics

All endpoints will be described using summary statistics for each treatment group, by visit where appropriate.

3.2.1 Summarizing Categorical Data

Categorical including binary data will be summarized by means of frequency counts and percentages. The denominator of percentages will be indicated if ambiguous. All categories will be displayed in summary tables including those with zero counts. A category of missing counts will be added.

3.2.2 Summarizing Continuous Data

Continuous data including scores will be summarized by means of arithmetic mean, standard deviation (SD), median, quartiles and ranges. Quartiles are given as *(lower quartile, upper quartile)* and ranges as *(minimum, maximum)*. The number of non-missing values will also be displayed.

3.3 Disposition of Subjects

A subject is screened if at least Visit 0 data are collected, randomized if Week 0 (Visit 1) data are collected and a randomization number given.

Subject disposition will be summarized by the number (counts and percentages) of patients

- screened
- failed screening
- randomized
- treated with an IP
- prematurely discontinued treatment
- completed treatment
- prematurely discontinued trial

Subject disposition will be summarized by treatment group and overall. Subject disposition will also be summarized per country and per site.

3.4 Premature Discontinuation of Treatment and/or Study Participation

On subject disposition (see Section 3.3) counts and percentages will also be given by reason for screen failure and premature discontinuation of treatment and/or trial participation, respectively.

3.5 Protocol Deviations

All observed protocol deviations will be listed. Following definitions in CTP Section 8.3 [1] and Section 4.2.3 below, protocol deviations will be classified as major or minor in a minuted meeting for blind review of the database conducted prior to final database lock and unblinding. All protocol deviations and major protocol deviations will be presented in frequency tables.

4 Study Specifications for Analysis

4.1 Interim Analysis

No interim analysis is planned.

4.2 Analysis Populations

4.2.1 Full Analysis Set

The full analysis set (FAS) includes all subjects randomly assigned to any IP following the intention-totreat principle. Subjects in the FAS are evaluated by treatment randomized to.

4.2.2 Safety Set

The safety set consists of all randomized subjects, excluding subjects who return all the trial medication sealed. Subjects in the safety set are evaluated by treatment actually administered.

4.2.3 Per-Protocol Set

The per-protocol set (PPS) includes all subjects of the FAS who complete the trial without major protocol deviations deemed to affect the primary endpoint analysis.

If at least one major protocol deviation is observed in a subject of the FAS, the subject will be excluded from the PPS. Decisions on excluding subjects from the PPS will be taken and documented before unblinding the study.

Subjects may be excluded from the PPS if any of the following criteria are met:

- Failure to meet key inclusion/exclusion criteria; i.e. deviation of inclusion/exclusion criteria that according to medical judgement may impact the primary endpoint analysis,
- Usage of restricted medications/treatments; i.e. medications/treatments that according to medical judgement may impact the primary endpoint analysis,
- Nonadherence to the visit schedule at Week 8: 49 to 66 days.
- Noncompliance with the trial treatment regimen; adherence to the treatment schedule defined as application of the randomized IP as specified by the investigator for at least 80% of the days from Week 0 to Week 8 visit, and at least 80% of the days from Week 4 visit to Week 8 visit.

4.2.4 Usage of Analysis Populations

The FAS will be used as randomized for all efficacy analyses. As randomized, the PPS will only be used in sensitivity analyses for the non-inferiority evaluations and for the PTCS score evaluation. PGA success on the scalp will only be analyzed in subjects that at Week 0 (Visit 1) has a PGA of psoriasis severity on the scalp assessed as at least mild and a scalp involvement of at least 0.3% BSA.

Safety endpoints will be analyzed in the safety set as treated, i.e. by trial medication actually taken.

Demographics and baseline disease characteristics will be described for the FAS, the safety set and the PPS. Other baseline characteristics, exposure and concomitant therapies will be described for the FAS.

4.3 Subgroups and Confounding Factors for Analysis

No subgroup analysis will be done.

The potential confounding by trial sites will be considered by adjustment in statistical models. By country, trial sites with less than 14 FAS subjects will be pooled to form *analysis sites*. For trial sites with 14 FAS subjects or more, the trial site will be the analysis site.

The potential confounding by PGA at baseline will be considered by adjustment in all statistical models.

Depending on the endpoint as described below, the analysis may be adjusted by further confounding factors, particularly the baseline values of the respective endpoints in the models as covariates.

4.4 Time Points and Time Periods

4.4.1 Periods, Visits and Study Days

The screening period will last from Screening (Visit 0) to randomization (Visit 1/Week 0, Day 0). The treatment period will last from randomization (Visit 1/Week 0) to end of treatment (Visit 6/Week 8 or Early Termination). The follow-up period will last from end of treatment (Visit 6/Week 8) to end of follow-up (Visit 7/Week 10).

Up to six on-site visits are scheduled per subject, at Screening (Visit 0), and Weeks 0, 1, 4, 6 and 8. Visit 1/Week 0 is Day 0, the reference date. In addition, at Week 2, there is a telephone contact planned. Another on-site visit, or a telephone interview, will be held at end of follow-up. Further unscheduled visits may be done as deemed necessary.

Per visit, actual study days will be derived as the time passed in number of days since the reference date plus 1.

4.4.2 Dates

The date of Visit 1 is the reference date, Day 0. Start and end dates, and the dates of last study drug application and last contact will be related to Day 0, given as *study day*. Negative study days indicate dates before Visit 1.

It is assumed that treatment in the treatment period occurs from the evening of Day 0 to the day before Visit 6 (Week 8) unless otherwise reported.

4.4.3 Identification of Baseline Values

Per variable, baseline values are the values reported at randomization (Visit 1/Week 0, Day 0). If values at randomization are missing, values at Screening (Visit 0) are considered as baseline values.

4.4.4 Definitions of Change from Baseline

Changes from baseline are defined as post-baseline value minus baseline value. Reductions are negative changes. Percentage changes from baseline are defined as 100 times changes from baseline divided by the baseline value.

4.4.5 Treatment Emergency of Adverse Events

An AE is treatment-emergent if it occurs or deteriorates at or after the first application of the IP. Otherwise, an AE is not treatment-emergent.

4.4.6 Treatment Relation of Concomitant Medication

A medication or therapy is related to treatment by timing. It is concomitant or post-treatment as defined in Section 2.4.4 above.

4.5 Units and Unit Conversion

Dates are recorded by day, month and year. For imputation of partial dates, see Section 4.7.1 below. Days are calculated following rules in Sections 4.4.1, 4.4.2 and 4.6.1.

It is assumed that no unit conversion is required. Laboratory data will be reported in or converted to SI units [8].

4.6 Data Derivations

For the derivation of total and sum scores in efficacy endpoints see Section 2.4.1 above. Age, in full years, is derived as the number of calendar years from year of birth to the year of screening.

4.6.1 Durations

Time durations, i.e. lengths of time periods, will be derived as end date minus start date plus 1 day in days.

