8.3 Analysis Populations

The analysis populations are defined as follows:

- Intent To Treat (ITT) population: all randomised subjects
- **Per Protocol (PP) population:** all subjects in the ITT population who complete the trial without any major protocol violations. The PP population will be determined and documented in blind review of the database conducted prior to un-blinding the trial database. Subjects may be excluded from the PP population if any of the following criteria are met:
 - Failure to meet key Inclusion/Exclusion criteria; i.e. violation of inclusion/exclusion criteria that according to medical judgement may impact the primary endpoint analysis
 - Usage of restricted medications/treatments; i.e. medications/treatments that according to medical judgement may impact the primary endpoint analysis
 - Nonadherence to the visit schedule at Week 8: -7/+10 days
 - Noncompliance with the trial treatment regimen; adherence to the treatment schedule defined as application of IP as specified by the investigator for at least 80% of the days from Day 1 to Week 8 visit, and at least 80% of the days from Week 4 visit to Week 8 visit
- **Safety population:** all randomised subjects who are dispensed the trial medication, excluding subjects who return all the trial medication unused.

Subjects in the ITT and PP populations will be analyzed as randomized, and subjects in the Safety population will be analysed as treated.

The ITT population will be used for the analyses of efficacy and other endpoints, while the Safety population will be used for all safety analyses. The PP population will be used in sensitivity analyses for the non-inferiority evaluations, and in a sensitivity analysis for the PCTS score evaluation.

MC2 Therapeutics

Confidential

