8.4 Estimands

The efficacy endpoints will be analyzed focusing on two different estimands:

Primary estimand (treatment-policy): the effect of initiating the treatment regimen in subjects with mild-to-moderate psoriasis, with or without any other psoriasis treatment, and whether or not the subject adhered to the treatment regimen.

Thus, for the treatment-policy estimand all available data will be used.

Secondary estimand (hypothetical-strategy): the expected effect in subjects with mild-to-moderate psoriasis if all subjects adhered to the treatment regimen and did not take any other psoriasis treatment (=treatment that according to medical judgement may improve psoriasis).

This is interpreted in the sense that subjects did not initiate other treatment that according to medical judgement may improve psoriasis, and for visits after baseline adhered to the treatment schedule defined as application of IP as specified by the investigator at the previous site visit for at least 70% of the days from baseline visit to Week 4, Week 4 to Week 6 and Week 6 to Week 8. For example, applying IP for 10 out of 14 days is considered adherence, while 9 out of 14 days is not. Thus, for the hypothetical-strategy estimand, only data at or prior to use of other treatment that may improve psoriasis according to medical judgement, and prior to non-adherence to treatment schedule is used. Missing data, data after use of other psoriasis treatment, and data after non-adherence is imputed.

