2.4.3 Extent of Exposure and Study Treatment Compliance

Records of IP used, and dosages administered will be kept during the trial. The *duration of study treatment* is derived as the time in days from the date of first study drug application to the date of last study drug application. The *extent of exposure* in days is determined as the duration of study treatment minus the number of days without dosing. The number of days without dosing is derived from dose documentation between the date of first study drug application and the date of last study drug application. Days without dosing are days with reported non-administration.

Subjects will be asked to return all used and unused tubes/bottles at each visit. All returned tubes/bottles that had been dispensed to a subject and are returned with a broken seal will be weighed to determine the amount of the IP used.

The *amount of drug used* in grams is derived as the sum of the difference in drug weight dispensed and returned per kit. The total amount of drug used will be evaluated and also the amount used during the first week, the three weeks from Week 1 to Week 4, and the four weeks from Week 4 to Week 8.

Duration of study treatment, extent of exposure, and amount of drug used will be presented by summary tables by treatment group.

Treatment Compliance

At all on-treatment visits, the subject will be asked if he/she has used the medication as prescribed. If this is not the case, the degree and nature of noncompliance will be collected in the CRF. In addition, subjects will be asked to complete a dosing diary during the treatment period as a measure of treatment compliance.

On a daily basis in the dosing diary, if non-administration due to approved discontinuation is reported, treatment compliance is concluded, and if missed administration is reported, treatment non-compliance is concluded.

For the entire treatment period to the Week 8 visit and for the periods from Week 0 to th Week 4 visit and from the Week 4 visit to the Week 8 visit, the percentage of *treatment compliance* is defined as 100 times the duration of the respective period minus the number of days with non-compliance divided by the duration of the respective period. Treatment compliance will be categorized to less than 80% versus 80% or more and to less than 70% versus 70% or more.

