4.6.2 Analysis Visit Windowing

Post-baseline visits are to be held at Weeks 1, 2, 4, 6, 8 and 10, namely at study Day 7, 14, 28, 42, 56 and 70, within two days from target day. In addition, unscheduled visits and visits of Early Termination may be given. Comprehensive non-overlapping visit windows are defined for Week 4 from Day 14 to Day 42 and for Week 8 as Day 43 or later, respectively, excluding any follow-up visits.

Primary and secondary efficacy endpoints will be summarized and analysed by *analysis visits*. For Week 4 and Week 8, analysis visits are defined as the visits held closest to the target day per analysis visit window as defined above. Any other visits within the same visit window will not be considered for analysis of primary or secondary efficacy endpoints. If the time distances of two visits from the target day are identical, the later visit is selected for analysis.

Other efficacy endpoints and safety endpoints will be summarized and analysed by nominal visits as appropriate.

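### The SAP's plus-one duration rule counts the Week 8 visit day, when no application is due, as a compliant day, so compliance is slightly inflated and the 80% per-protocol rule is loosened at some visit spacings

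*SAP*

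**What the plan says.** SAP 2.4.3 defines percentage compliance as "100 times the duration of the respective period minus the number of days with non-compliance divided by the duration of the respective period", for three periods: Week 0 to the Week 8 visit, Week 0 to the Week 4 visit, and the Week 4 visit to the Week 8 visit. A day lowers the percentage only through the diary: "if missed administration is reported, treatment non-compliance is concluded". SAP 4.6.1 gives the general counting rule: "Time durations, i.e. lengths of time periods, will be derived as end date minus start date plus 1 day in days". SAP 4.5 refers to that section for calculating days, and no exception is made for compliance.

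On when doses are due, SAP 4.4.2 assumes that "treatment in the treatment period occurs from the evening of Day 0 to the day before Visit 6 (Week 8"), unless otherwise reported. SAP 4.4.1 ends the treatment period at Visit 6. Protocol Table 7-1 shows product and diary returned at Week 8 and none dispensed.

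Two thresholds use these counts. The per-protocol set (SAP 4.2.3) requires application "for at least 80% of the days from Week 0 to Week 8 visit", and the same share from Week 4 to Week 8. The hypothetical strategy (SAP 5.3) sets 70% for Day 0 to Week 4, Week 4 to Week 6 and Week 6 to Week 8. Protocol 8.4 illustrates the 70% rule for a two-week interval: "applying IP for 10 out of 14 days is considered adherence, while 9 out of 14 days is not". Protocol 8.3 words the 80% rule as "application of IP as specified by the investigator for at least 80% of the days from Day 1 to Week 8 visit".

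**The concern.** Taken together, these sections put a day into the compliance ratio on which the SAP assumes no application. Only a reported missed administration lowers the ratio, so that day enters both numerator and denominator as compliant. Adding 1 to both can only raise a ratio below 100%. In periods ending at Week 8, any resulting change of class therefore runs from non-adherent to adherent.

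The ratio informs who stays in the per-protocol set. If the same formula is carried over to the 70% rule, it also decides which data are valid under the hypothetical strategy. These are two of the three sensitivity analyses of the primary endpoint in SAP 5.5.1. Both are meant to show the result in subjects who used the product, so keeping subjects who miss the threshold works against their purpose. The tabulated compliance percentages are affected as well.

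**Working it through.** **Inputs.** Nominal visit days are 0, 28, 42 and 56 (visits are due "namely at study Day 7, 14, 28, 42, 56 and 70, within two days from target day"). The duration rule is SAP 4.6.1, the compliance formula SAP 2.4.3, and the last dosing day SAP 4.4.2. Let *n* be the dosing days in a period (end date minus start date) and *m* the missed days. Counting days on which an application was due gives (n - m)/n. The SAP rule gives (n + 1 - m)/(n + 1).

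**Protocol example first.** With n = 14, 10/14 = 71.4% (adherent) and 9/14 = 64.3% (not adherent), which reproduces Protocol 8.4. Under the plus-one count these become 11/15 = 73.3% and 10/15 = 66.7%. The classes stay the same; only the day count differs, 15 against 14.

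**Nominal visits, periods ending at Week 8.**
- Week 0-8: 56 doses due, denominator 57. Up to 11 missed days pass under either count (45/56 = 80.4%; 46/57 = 80.7%). Twelve fail under either (44/56 = 78.6%; 45/57 = 78.9%), a rise of 0.4 points.
- Week 4-8: 28 doses due, denominator 29. Up to 5 missed days pass under either count (23/28 = 82.1%; 24/29 = 82.8%). Six fail under either (22/28 = 78.6%; 23/29 = 79.3%), a rise of 0.7 points.

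No class changes here.

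**Off-nominal visits.** At 80%, a class changes only if a whole number *m* satisfies n/5 < m ≤ (n + 1)/5, that is, when n + 1 is a multiple of 5. At 70%, the condition is 0.3n < m ≤ 0.3(n + 1).

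| Period, rule | n | m | Due-day count | SAP count |
|---|---|---|---|---|
| Week 4-8, 80% | 24 | 5 | 19/24 = 79.2% | 20/25 = 80.0% |
| Week 4-8, 80% | 29 | 6 | 23/29 = 79.3% | 24/30 = 80.0% |
| Week 0-8, 80% | 49 | 10 | 39/49 = 79.6% | 40/50 = 80.0% |
| Week 0-8, 80% | 54 | 11 | 43/54 = 79.6% | 44/55 = 80.0% |
| Week 0-8, 80% | 59 | 12 | 47/59 = 79.7% | 48/60 = 80.0% |
| Week 0-8, 80% | 64 | 13 | 51/64 = 79.7% | 52/65 = 80.0% |
| Week 6-8, 70% (inferred) | 13 | 4 | 9/13 = 69.2% | 10/14 = 71.4% |
| Week 6-8, 70% (inferred) | 16 | 5 | 11/16 = 68.8% | 12/17 = 70.6% |

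The Week 0-8 rows cover the per-protocol window of Day 49 to 66; within ±2 days only n = 54 applies. With both visits inside ±2 days there are 25 pairs of visit days. Five of them (Week 4-8) and seven (Week 6-8) give a length in the table. Even then, only a subject with that one missed-day count changes class.

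**Visit days shared by two periods.** At Weeks 4 and 6 an evening dose is due on the visit day, and the plus-one rule places that day in both adjoining periods. A miss on that day then counts twice, which can push a subject the other way. Week 0-4 at nominal dates, with 8 misses on Days 0-27 and one on Day 28: 20/28 = 71.4% by due days in the period, but 20/29 = 69.0% under the SAP count, below 70%.

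**How many subjects (illustration only).** The documents give no miss rate. I assumed a beta-distributed miss probability between subjects (concentration 2 to 100) and visits uniform within ±2 days. With a mean of 5-10% missed days, a simulation puts 0.15-1.2% of subjects (about 1 to 6 of 476) wrongly above the 80% rules. At a mean of 17% the share reaches at most 2.8% (about 13). No subject moved the other way on the 80% rules.

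**The case against.** The strongest reply is that plus one is the ordinary inclusive count, and that the SAP merely leaves the end of the period open. If a period ended on the last assumed dosing day, Day 55, the rule would give 55 - 0 + 1 = 56 and no error. The protocol's Day 1 to Day 56 also makes 56 days only by inclusive counting. But SAP 2.4.3 runs its periods to the Week 8 visit and SAP 4.4.1 ends the treatment period at Visit 6, so the alternative end date is not what is written. The protocol's 56 equals the number of doses due; the SAP's 57 does not.

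Several limits do stand:
- A reader might infer that the SAP overturns the protocol's 14-day example. It does not: both outcomes are preserved, and only the day count differs.
- A reader might infer that every error favours adherence. That holds for the 80% rules and for Week 6-8, but not for the earlier intervals of the hypothetical strategy.
- SAP 2.4.3 gives no formula for Week 4-6 or Week 6-8. SAP 5.3 says only that non-adherence is derived from days with non-compliance, so applying the duration rule there is an inference.
- Subjects *may* be excluded from the per-protocol set, with deviations classified at blind review, so the ratio informs that decision rather than making it alone.
- SAP 4.4.2 allows for reports to the contrary and evening use is only preferred, so a dose on the Week 8 visit day is unlikely rather than impossible.

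**Conclusion.** Wrong as written, but minor. Read together, SAP 2.4.3, 4.4.1, 4.4.2 and 4.6.1 give a denominator one day longer than the number of doses due in periods ending at Week 8, and they credit that day as compliant. The inflation is about 0.4 points (Week 0-8) and 0.7 points (Week 4-8) near 80%. Misclassification for the per-protocol set needs one of a few off-nominal lengths together with one exact missed-day count, and the subjects concerned have a true ratio between 79% and 80%. The effect on the 70% rule is conditional on the same formula being used there, and could run in both directions across the three intervals.

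The number of subjects rests on assumed adherence and visit timing; it is likely a few unless doses are missed often. A reader might infer that the non-inferiority conclusion is at risk. The documents do not support that: the primary analysis uses all randomised subjects under the treatment-policy strategy and no compliance ratio, and SAP 5.3 keeps sensitivity analyses outside the hierarchical testing. No effect on an estimate or confidence interval has been shown.

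**What to change.** Add to SAP 2.4.3, as an exception to SAP 4.6.1:

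> For compliance, the denominator of a period is the number of days on which an application was due, from the start visit date to the day before the end visit date (end date minus start date, without adding 1). Each day belongs to one period only.

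State that this count serves both the 80% and the 70% rules, and extend it explicitly to Week 4-6 and Week 6-8. This restores 14 days for a two-week interval, as in Protocol 8.4, and 56 for Week 0-8. The SAP's Week 0 start and the protocol's Day 1 start for the 80% rule should be aligned in the same edit.

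The cost is one or two sentences and one line of derivation code. A few subjects may leave the per-protocol set. The change should be made before the blind review, because SAP 4.2.3 requires exclusions to be documented before unblinding.
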